4.9 Analyses

For descriptive analysis of parameters, see section 4.7 above. In the following, analysis of the endpoints is described in detail.

The effect of exposure to EMPAGLIFLOZIN on the risk of ketoacidosis, severe urinary tract infections, volume depletion and dehydration compared to those exposed to DPP-4 inhibitor will be estimated. Hence, the following is applied to each of the four outcomes of interest.

The endpoints will be analysed in the index period (primary), in the index period during Ramadan (secondary), in the follow-up period and in the follow-up period during Ramadan.

Estimation of propensity scores

In a preparatory step, for each patient, propensity scores (PS) will be estimated by means of logistic regression, estimating the likelihood of a patient receiving Empagliflozin based on prior and baseline confounders predictive of treatment. The statistical model will be built by a selection process optimizing the goodness of fit.

At first, the relationship between treatment (EMP, DPP-4 inhibitor) and all potential clinical confounder candidates will be tested in bivariate analyses. Based on the type of the candidate, Fisher's exact tests or Student's t-tests will be applied [Heiberger 2015]. In case of distributional constraints, χ^2 tests or Mann-Whitney U tests may be alternatively applied, respectively.

Clinically relevant confounder candidates include age, gender, body mass index (BMI), blood pressure, fasting blood glucose level at baseline, and baseline HbA1c, if available, comorbidity indicators like hypertension, dyslipidaemia, kidney diseases, kidney stones, history of kidney transplant, liver diseases, prostate diseases, pancreatitis, surgery, infections (other than UTIs) and heart diseases, if available, genital defects, urinary tract anatomical defects, laboratory measurements and relevant prior and concomitant medications at baseline. Relevant prior medications in the last 6 months and at baseline include insulin sulfonylureas, meglitinides, thiazolidinediones, α -glucosidase inhibitors, glucagon-like peptide-1 receptors, antihyperlipidemics (statins, fibrates, niacin), antihypertensive agents (diuretics, ACE inhibitors, beta blockers), antipsychotic medications, corticosteroids, tacrolimus, glucagon, interferon,

Statistical Analysis Plan (SAP)

Document Date: 17APR2019

Document Version: 1.0 Final

albuterol, dopamine, dobutamine, terbutaline and ritodrine. However, candidates cannot be considered if unknown or missing in a significant number of patients.

If the p-value of bivariate analysis is lower than 0.25, confounder candidates will be included in an initial multivariate logistic regression model. By backward elimination, or other appropriate methods of model selection, the model will be optimized to yield a final model.

The resulting PS will be described by group by means of a summary table. The distribution of the PS will be plotted for the two treatment groups (EMP, DPP-4 inhibitors) to see whether there are any areas where there is no overlap. The estimates of treatment effect may not be reliable in areas where there is no overlap. The area with overlap is called the common support region. It may be necessary to remove subjects outside of the common support region (e.g. extreme tails of the PS distribution) before analysis.

The effect of the confounders in bivariate testing and in the initial and final models will be described by p-values.

PS-based Analysis

Based on those PS, the main analysis approach is stratification to control for confounders,

The stratification will divide the entire study population into five groups by PS quintiles based on their PS value. Quintiles will be used for analysis if the number of patients are sufficiently balanced per group within strata and if the confounding covariates are balanced. Balance will be reviewed graphically and, depending on the scale of the covariate, by Mantel-Haenszel and other applicable tests of confounding covariates of the final model by strata. If, due to significantly low p-values from Mantel-Haenszel and other applicable tests, the balance based on quintiles is insufficient, the number of strata will be increased. Balance investigations will be repeated and the number of strata further increased until a reasonable degree of balance is achieved. It may also be necessary to remove patients from extreme tails of the PS distribution.

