7. RATIONALE AND BACKGROUND

Around 415 million patients are affected by DM worldwide. DM is considered an epidemic in many countries of the world, and the number of people affected is expected to double over the next decade. [R16-4703] DM is a major leading cause of many complications and diseases such as heart diseases and several types of infections. T2DM is more common than type 1, comprising 90-95% of all DM cases. [R17-3422] Over 5 million people died from DM in 2015 worldwide. In the Middle East and North Africa, around 36 million patients were affected by DM in 2015, a number expected to rise to 72 million patients by 2040. Saudi Arabia has one of the highest prevalence of DM in the world with over 20% of the population affected. [R16-4703]

Empagliflozin is a selective sodium/glucose co-transporter 2 (SGLT2) inhibitors one of the most recent classes of drugs used to treat T2DM. SGLT2 inhibitors promote the renal excretion of glucose and help lower elevated blood glucose levels in patients with T2DM. [P14-06594] In Saudi Arabia, It is indicated for treatment of T2DM as monotherapy or add-on combination therapy. It is used as monotherapy when exercise and diet control alone do not provide glycaemic control in patients for whom use of metformin is considered inappropriate because of intolerance. It is also used in combination with other glucose lowering agents—including insulin—when they do not provide adequate glycaemic control. [R17-3413] Several clinical trials showed the efficacy of Empagliflozin in reducing the blood glucose level. Furthermore, Empagliflozin is a unique drug among all hypoglycaemic agents because it has shown a reduction in major cardiovascular events, which has not been the case with other oral hypoglycaemic agents. Empagliflozin, as other SGLT2 inhibitors, is associated with some adverse reactions such as urinary tract infections and genital infections, especially in females. In addition, rare cases of diabetic ketoacidosis (DKA) have been reported. [P15-03461], [P13-09179], [P15-05613] In parallel to the launch of SGLT2 inhibitors in Saudi Arabia, the Saudi Food and Drug Authority (SFDA) has requested a non-interventional study to further monitor the safety of Empagliflozin in the country, including during the Ramadan period.

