9.2.2.1 Visit 1; Baseline Visit

Upon patient enrolment, the following available data will be recorded on the patient's e-CRF.

- Visit date
- Diagnosis: date of the diagnosis of T2DM, Family history of T2DM
- Inclusion / Exclusion criteria

- Informed consent form: Date of Informed consent
- Demographic data: Age, gender,
- Diabetes mellitus related complication (Retinopathy, Neuropathy, Nephropathy)
- Medical history: Hypertension, Dyslipidaemia, Coronary artery disease, Stroke, Liver disease, Renal failure, Renal Transplant, Renal Stones Nephropathy, Prostate Diseases, Pancreatitis, Diabetic ketoacidosis, Surgery, Infections (other than UTIs) and heart diseases, other (history of concomitant disease within 6 months). In addition, genital defects, urinary tract anatomical defects, when available.
- Baseline lab variables when available – Complete Blood Count (CBC), Oral Glucose Tolerance Test (OGTT), ketones level, amylase, lipase, arterial blood gas, pH, bicarbonate, lipid profile tests, Blood Urea Nitrogen (BUN), liver tests, International Normalized Ratio (INR) for prothrombin time and platelets
- Physical examination: body mass index (BMI), blood pressure, pulse rate, weight
- Baseline HbA1C, blood glucose level (if available)
- Renal Function: record Serum creatinine, eGFR, urine ACR if results are available (collected within the latest 2month period) (if available)
- Concomitant anti-hyperglycemic agent: record any anti-hyperglycemic agents have been taken prior to the baseline visit (within 6 months prior to baseline)
- Concomitant medications: record all medications have been taken at least once since one month prior to the baseline visit.
- Dose of Empagliflozin / DPP4-Inhibitor given
- PASS physician's electronic signature for data integrity

At visit 1, the patient will be requested to contact the treating physician in the event of any adverse events noted after initiating Empagliflozin or the comparator DPP-4 inhibitor treatment.

9.2.2.2 Visit 2; 16±2 weeks from Visit 1

After 16±2 weeks from Visit 1, the patients will return for follow-up. The followings will be noted and recorded in the e-CRF.

- Visit date
- Physical examination: blood pressure, pulse rate, weight (if available)
- HbA1C (if available)
- Any change of Empagliflozin or comparator DPP-4 inhibitor given
- Concomitant anti-hyperglycemic agent including new medications taken since last visit: any change in the concomitant medications (dose and dosing intervals)

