9.3.4 Covariates

The covariates of interest are age, gender, body mass index (BMI), blood pressure, blood glucose level, and HbA1c, if available. Comorbidities of interest include hypertension, dyslipidaemia, kidney diseases, kidney stones, history of kidney transplant, liver diseases, prostate diseases, pancreatitis, surgery, infections (other than UTIs) and heart diseases, if available. In addition, genital defects, urinary tract anatomical defects, lab variables (CBC, FPG, OGTT, ketones level, amylase, lipase, arterial blood gas, pH, bicarbonate, ScCr, lipid profile tests, BUN, liver tests, INR and platelets) and concomitant medications [REDACTED] will be considered as covariates. All these covariates will be identified, if available, for all cohort members prior to and including the index date. Severity of T2DM will be assessed by HbA1c values, concomitant diagnoses and duration since the first diagnosis, when available.

These and other variables that can differ by exposure group will be considered for inclusion as predictors in the logistic regression models used to generate the propensity scores.

Propensity scores will be used in the analysis to quantify the probability of receiving Empagliflozin at the index date for new users of both Empagliflozin and DPP-4 inhibitors.

At the index date, cohort members will also be classified by indicator variables on the calendar time of cohort entry (by quarter) whether the index treatment (Empagliflozin or DPP-4 inhibitor) was added to existing medication (adding on), or if the index treatment was initiated as a replacement for another GLD (switching from the existing GLD to Empagliflozin or DPP-4 inhibitor), and whether this treatment was received as monotherapy or as dual or triple therapy. A variable indicating whether or not patients were receiving insulin at the index date will also be created.

List of Variables, (other variables will be added during the study period)

Demographics

1. Age
2. Gender

Hospitalization, when available

3. Admission date
4. Place admitted from
5. Outcomes diagnosis date
6. Place of diagnosis (ER, Inpatients, Outpatient)

Treatment

7. Treatment initiation date
8. Treatment discontinuation date

Outcomes, when available

9. Date of DKA diagnosis
10. Date of UTI diagnosis
11. Date of dehydration diagnosis
12. Date of volume depletion diagnosis
13. Date of death
14. Primary cause of death
15. Date of discharge
16. Date of admission
17. Reason for admission

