39. BUN

Comorbidities, Medical History

40. Diabetes
41. Kidney diseases
42. Hypertension
43. Heart failure
44. Acute coronary diseases
45. Heart diseases
46. Diabetic ketoacidosis

47. Pregnancy
48. Abdominal trauma
49. Kidney stones
50. Body paralysis (paraplegia or quadriplegia)
51. Pancreatitis
52. Dyslipidaemia
53. Cerebrovascular disease
54. Pulmonary disease
55. Hypothyroidism
56. Hyperthyroidism
57. Surgery
58. Liver disease

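### History of diabetic ketoacidosis is collected but not named among the SAP's propensity-score candidates, so adjustment for it in the ketoacidosis comparison is allowed but not assured

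*SAP*

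**What the plan says.** **Collection.** Protocol 9.2.2.1 (Visit 1) records medical history including "Prostate Diseases, Pancreatitis, Diabetic ketoacidosis, Surgery, Infections (other than UTIs) and heart diseases". The numbered List of Variables in protocol 9.3.4 (Covariates) carries "46. Diabetic ketoacidosis" under comorbidities and medical history.

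**Covariates in the protocol text.** The opening paragraph of 9.3.4 says "Comorbidities of interest include hypertension, dyslipidaemia, kidney diseases, kidney stones, history of kidney transplant, liver diseases, prostate diseases, pancreatitis, surgery" and goes on to infections and heart diseases. Prior ketoacidosis is not in that sentence. The section then adds: "These and other variables that can differ by exposure group will be considered for inclusion as predictors in the logistic regression models".

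**Candidates in the SAP.** SAP 4.9 repeats essentially the same comorbidities, introduced as "comorbidity indicators like hypertension, dyslipidaemia, kidney diseases, kidney stones, history of kidney transplant, liver diseases, prostate diseases, pancreatitis". It also names many individual drugs. Prior ketoacidosis does not appear. The same section says that "all potential clinical confounder candidates will be tested in bivariate analyses".

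**Selection.** SAP 4.9: "If the p-value of bivariate analysis is lower than 0.25, confounder candidates will be included in an initial multivariate logistic regression model". Backward elimination or another selection method then yields the final model. Protocol 9.7.1 has the same 0.25 threshold. Within-stratum balance tests are planned for the covariates of the final model.

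**Outcome models.** SAP 4.9.1 says that these models may include the treatment-confounding candidates and will include season and other effects still to be short-listed.

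**The concern.** Ketoacidosis is the first-listed primary outcome, and a previous episode is an obvious candidate predictor of another. The protocol's background (section 7) notes for SGLT2 inhibitors that "rare cases of diabetic ketoacidosis (DKA) have been reported", and section 9 leaves the choice of drug to the physician. A physician could reasonably steer a patient with past ketoacidosis towards a DPP-4 inhibitor. Prior ketoacidosis is not a named exclusion.

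If that steering occurs and is not adjusted for, the comparator group carries more high-risk patients, its ketoacidosis rate rises, and the empagliflozin-to-DPP-4 IRR falls below its true value. In a safety study requested by a regulator, an error in that direction matters more than one in the other.

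The selection rule adds to this. It keeps variables by the strength of their association with treatment in the sample. A rare history that strongly predicts the outcome can show a weak p-value for treatment and still confound.

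**Working it through.** **Step 1: follow the variable through the documents.**

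| Place | Prior ketoacidosis named? |
|---|---|
| Protocol 9.2.2.1, Visit 1 medical history | Yes |
| Protocol 9.3.4, opening paragraph | No, but further variables are allowed |
| Protocol 9.3.4, List of Variables | Yes, item 46 |
| SAP 4.9, candidate list | No, but the list is illustrative |
| SAP 4.9.1, outcome models | No, but further effects may be added |

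The variable is available and permitted. At no point is it required to enter a model.

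**Step 2: would a rare history pass the p < 0.25 screen?** The group size of 750 is from protocol 9.5. Fisher's exact test is one of the tests named in SAP 4.9. For observed counts (empagliflozin v DPP-4 inhibitor, each of 750):

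- 1 v 4: p = 0.37, dropped
- 2 v 6: p = 0.29, dropped
- 4 v 8: p = 0.39, dropped
- 2 v 15: p = 0.002, kept

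**Step 3: size of the bias if the variable is left out.** For a binary confounder with prevalence pE (empagliflozin) and pD (DPP-4 inhibitor) that multiplies the ketoacidosis rate by R, the IRR is multiplied by

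B = [1 + pE(R − 1)] / [1 + pD(R − 1)].

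The documents give no value for pE, pD or R. The values below are assumptions for illustration. The chance of passing is the exact probability that Fisher's test gives p < 0.25, summed over two independent binomial counts with n = 750 each.

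| pE v pD | B at R = 10 | B at R = 20 | Chance of passing |
|---|---|---|---|
| 0.5% v 1% | 1.045/1.090 = 0.96 | 1.095/1.190 = 0.92 | 38% |
| 0.2% v 1% | 1.018/1.090 = 0.93 | 1.038/1.190 = 0.87 | 74% |
| 0.5% v 2% | 1.045/1.180 = 0.89 | 1.095/1.380 = 0.79 | 91% |
| 0.2% v 2% | 1.018/1.180 = 0.86 | 1.038/1.380 = 0.75 | 99% |

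**Step 4: read the columns together.** Where the screen often fails (first two rows), the bias is modest, at 0.87 to 0.96. Where the bias is large (last row, R = 20), the screen would nearly always keep the variable if it were tested at all. The plan has no figure of its own to reproduce here: the sample size is set by regulatory requirement, with no stated event rate or effect size.

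**The case against.** The strongest reply is that the plan already allows this adjustment. Item 46 stands inside the protocol's Covariates section, and that section lets further variables into the propensity score. The SAP list is illustrative, the SAP undertakes to test every potential clinical confounder, and SAP 4.9.1 offers a second route through the outcome models. All of this stands. A reader might infer from the missing name that the ketoacidosis comparison has no protection against such steering, or that the protocol's covariate section overlooks the variable. The documents support neither inference.

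A reader might also take the factor of 0.75, under which a true excess of 33% (1/0.752 = 1.33) would show as an IRR of 1.0, as the likely consequence of the screen. It is not. In that scenario the variable passes 99% of the time, so the factor applies only if the variable is never considered or is eliminated later.

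Steering is itself an inference: the documents report rare cases and physician choice, not prescribing by this history. The study excludes patients for whom either drug is contraindicated under the local label. The label text is not in the documents, so the patients at issue may already be outside the study. Finally, protocol 9.9 concedes that the number of patients may be too low to assess the risk of ketoacidosis. A shift of 4-13% is likely to be small beside the width of the interval.

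What remains is that permission does not settle the matter. The SAP should say in advance whether prior occurrence of a primary outcome is adjusted for. As written, that depends on an unstated choice of candidates and on a p-value for association with treatment. A variable that falls out has no planned within-stratum balance test.

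**Conclusion.** The point holds as a limited gap in pre-specification. The SAP does not carry the collected variable by name into its candidates, and its selection rule can drop it.

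Under the assumed inputs, the IRR for ketoacidosis would be multiplied by about 0.87-0.96 in the settings where the screen often fails. The direction is towards reassurance if patients with the history are steered to DPP-4 inhibitors, and it reverses if the steering runs the other way. The size depends wholly on prevalences and a rate ratio that the documents do not give, and it is nil if the label already keeps these patients out. The change is worth making because it costs almost nothing and concerns the first-listed outcome.

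**What to change.** In SAP 4.9:

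1. Name history of diabetic ketoacidosis among the propensity-score candidates.
2. For the ketoacidosis analysis, retain it in the propensity-score model, or in the ketoacidosis outcome model, whatever its p-value. Because protocol 9.7.1 limits inclusion to p < 0.25, record an exception for the propensity score in SAP 4.10.
3. Report its balance in the planned Table 15.17.
4. Add one sensitivity analysis: the ketoacidosis IRR without patients who have the history. If one group has no such patients, so that the coefficient cannot be estimated, rely on this restricted analysis.

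The protocol 9.3.4 variable list needs no change, and no new data are required. The cost is a few lines of SAP text, one extra covariate and one extra run.

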This study will be carried out in the manner of successive surveys that the investigator will be asked to successively write in the case report forms (e-CRFs) from each subject who was initially administered the drug following the study start date until the requested number of subjects is reached. Number of recruited patients will be comparable in each group within a given timeframe (i.e. each site will ensure to recruit similar number of patients for each group according to assigned blocks of enrolment).

Prior to initiation of the study, a written contract shall be concluded, and this contract shall be executed among BI OPU, CRO with the head of the site or the investigator with his/her consent.

Patients will be managed according to the local practice guidelines. The choice of treatment will be solely at the discretion of the participating physician. Empagliflozin and the comparator DPP-4 inhibitor will be administered according to the approved labels in Saudi Arabia. [R17-3427] Hence there are no additional risks to patients by participating in this PASS.

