9.5 STUDY SIZE

The sample size is of 1500 patients; it is based on SFDA requirements. As per SFDA regulation and requirements to detect the DKA cases, 750 patients will be enrolled in each group (DPP4i and SGLT-2i). The number of recruited patients will be comparable in each group within a given time frame (i.e. each site will ensure to recruit similar number of patients for each group according to assigned blocks of enrolment). In addition, prevalence of the primary outcomes was searched in literature and a study found assuming the prevalence to be around 25% (urinary tract infection and other risk factors) among Saudi patients with diabetes.

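### Prior urinary tract infection is left out of the named confounders although severe UTI is a primary outcome; the plan permits adjustment for it but does not commit to it or to a within-stratum balance check

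*SAP*

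**What the plan says.** Severe UTI, meaning pyelonephritis or urosepsis, is one of four primary outcomes (protocol 8.1 and 9.3.3; SAP 2.1 and 4.7.5). UTI history is excepted in three linked places:

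- Protocol 9.2.2.1, Visit 1 medical history: "Diabetic ketoacidosis, Surgery, Infections (other than UTIs) and heart diseases, other (history of concomitant disease within 6 months".
- Protocol 9.3.4, covariates: "infections (other than UTIs) and heart diseases, if available".
- SAP 4.9, propensity-score candidates: "infections (other than UTIs) and heart diseases, if available, genital defects, urinary tract anatomical defects".

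In the numbered variable list of protocol 9.3.4, UTI appears only among the outcomes, as "Date of UTI diagnosis". The comorbidity part of that list has no UTI item.

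Several passages leave room for prior UTI. Visit 1 has an entry for other recent concomitant disease. Protocol 9.3.4 says "These and other variables that can differ by exposure group will be considered for inclusion as predictors in the logistic regression models". SAP 4.9 gives its comorbidities as examples. SAP 4.9.1 says the outcome models will contain covariates that may affect the outcome, some still to be chosen. Medical history is mandatory at Visit 1 (SAP Table 3-1), and it is MedDRA-coded and tabulated (SAP 4.7.2) by treatment group (SAP 4.5.1).

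Under SAP 4.9, a candidate enters the initial propensity model if its bivariate p-value is below 0.25 and then faces backward elimination. Candidates missing in many patients are dropped. The balance tests by stratum cover the confounders of the final model.

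**The concern.** Prior UTI meets both conditions for a confounder on the protocol's own account. It can influence prescribing: the protocol states of empagliflozin that it "is associated with some adverse reactions such as urinary tract infections and genital infections, especially in females", and that "The choice of treatment will be solely at the discretion of the participating physician". It also plausibly predicts severe UTI. Propensity-score stratification is the main means of control for confounding, and the named lists that feed it take this history out.

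The adjusted severe-UTI rate ratio is a main safety result. If UTI-prone patients tend to receive DPP-4 inhibitors, the ratio is pulled down and a modest harm could look like none. If they tend to receive empagliflozin, it is pulled up. The planned crude history table by group could hint at an imbalance. It could not show whether the imbalance remains within strata, and because the only named infection item excepts UTI, capture at Visit 1 may be incomplete.

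**Working it through.** The documents give no figure for this point, so there is none to reproduce. What follows is an illustration on assumed inputs.

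**1. Size of the possible bias.** For one unadjusted binary confounder, the ratio of observed to true rate ratio is

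B = [1 + p1(RR − 1)] / [1 + p0(RR − 1)],

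where p1 and p0 are the shares with prior UTI on empagliflozin and on DPP-4 inhibitors, and RR is the effect of prior UTI on severe UTI. The formula treats prior UTI as independent of the adjusted covariates.

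The only related figure is in protocol 9.5: "a study found assuming the prevalence to be around 25% (urinary tract infection and other risk factors) among Saudi patients with diabetes". It is ambiguous and is not a frequency of UTI history, so 25% serves only as an assumed upper prevalence. RR is assumed to be 2 to 5.

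| p1 v p0 | RR 2 | RR 3 | RR 5 |
|---|---|---|---|
| 20% v 25% | 0.96 | 0.93 | 0.90 |
| 15% v 25% | 0.92 | 0.87 | 0.80 |
| 10% v 25% | 0.88 | 0.80 | 0.70 |

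With the groups swapped, the range is 1.25/1.20 = 1.04 to 2.00/1.40 = 1.43. With equal shares B = 1.

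Mid case (15% v 25%, RR 4): 1.45/1.75 = 0.83. A true ratio of 1.2 would be seen as 1.2 × 0.83 = 0.99.

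**2. Comparison with sampling error.** Assume 0.5% to 2% of 750 patients per group have severe UTI, which is 3.75 to 15 events per group. The standard error of the log rate ratio is √(2/events) = 0.73 to 0.37. The 95% interval is then a factor of exp(1.96 × 0.73) = 4.2 down to 2.1 each way. The mid-case bias, |ln 0.83| = 0.19, is 0.26 to 0.52 of one standard error. The 0.70 extreme is 0.49 to 0.98 of one.

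**3. Would listing it as a candidate be enough?** Simulated Fisher tests with 750 per group give these chances of passing the p < 0.25 screen:

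| True shares | Fully recorded | Half recorded |
|---|---|---|
| 25% v 20% | 0.86 | 0.63 |
| 10% v 8% | 0.55 | 0.38 |

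A real imbalance could therefore be screened out, and prior UTI would then also drop out of the balance tests.

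**4. Would forcing it in be safe?** Split patients into recorded and not-recorded prior UTI and combine by Mantel-Haenszel, assuming no false entries. In the mid case:

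| Recorded, empagliflozin v DPP-4 | Residual factor |
|---|---|
| 50% v 50% | 0.90 (better than 0.83) |
| 60% v 40% | 0.84 |
| 70% v 30% | 0.79 (worse than 0.83) |

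For 70% v 30%, take one unit of person-time per group and a baseline rate of 1. The recorded stratum has person-time 0.105 and 0.075 and adds 0.175 to both sums. The other stratum has person-time 0.895 and 0.925 and events 0.045 × 4 + 0.85 = 1.03 and 0.175 × 4 + 0.75 = 1.45. The ratio is (0.175 + 1.03 × 0.925/1.82) / (0.175 + 1.45 × 0.895/1.82) = 0.698/0.888 = 0.79.

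With 20% prior UTI in both groups, so no true imbalance, the same 70% v 30% recording gives 0.711/0.818 = 0.87. The adjustment creates a bias where there was none.

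**The case against.** The strongest reply is that the plan is open rather than closed. A reader might infer that it forbids adjustment for prior UTI. It does not: the open wording in both documents allows a recorded prior UTI to be used, and mandatory coded history could show it. What stands against this reply is that none of these passages commits to adjustment or to a balance check, while an exception repeated three times points the other way.

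A reader might also infer that UTI is singled out because prior ketoacidosis is named. That holds only for Visit 1 and the numbered variable list. Prior ketoacidosis is also not named in the covariate paragraph of protocol 9.3.4 or among the SAP 4.9 candidates. Only the explicit exception is particular to UTI.

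It is fair to say that the effect may be small. No document figure supports any imbalance or risk ratio. Gender, kidney disease, stones, prostate disease, and genital and urinary tract defects are candidates and would carry part of the effect. Sampling error probably dominates. This limits the weight of the point but does not remove it, because a confidence interval does not convey confounding.

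The e-CRF is not among the documents and may hold a separate UTI field. Parts of the SAP are also not visible. Nothing is inferred from either.

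**Conclusion.** The point holds as a gap in commitment. Prior UTI is excepted wherever infection history is named, and nothing obliges the analyst to adjust for it or to check it within strata, so the severe-UTI rate ratio may be confounded. The documents do not support the stronger conclusion that the ratio is biased, or that it is biased towards making empagliflozin look safe.

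The illustrative range is 0.70 to 0.96, or 1.04 to 1.43 with the imbalance reversed. It rests on assumed prevalences of 10% to 25%, an assumed risk ratio of 2 to 5 and no help from measured correlates. On the assumed event rates, the bias is less than one standard error throughout the 0.70 to 0.96 range. The change is worth making because it is cheap and this is a regulator-requested safety study. Forced inclusion in the primary model is not supported, since its benefit depends on similar recording in both groups.

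**What to change.** 1. In SAP 4.9, delete the UTI exception. Name prior UTI (any; and pyelonephritis or urosepsis) as a confounder candidate, taken from the MedDRA-coded medical history with onset before the index date.
2. Report recorded prior UTI by group, with its standardised difference overall and within propensity-score strata, in Table 16.17 (the severe-UTI counterpart of Table 15.17), whether or not it enters the final model.
3. Add a severe-UTI sensitivity analysis that keeps recorded prior UTI in the propensity model regardless of the p < 0.25 screen and backward elimination. Code patients without an entry as having no recorded prior UTI. Show the result beside the main one.
4. Add a quantitative bias analysis for severe UTI in both directions, over a stated grid that includes recording that differs between groups. It fits the sensitivity analyses for bias and confounding already promised in the protocol abstract. State incomplete and possibly differential capture as a limitation.

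The cost is SAP wording, extra rows in a planned table and two sensitivity analyses. The downside is that adjustment on unevenly recorded history can worsen or create bias, which is why step 3 stays outside the primary model. Changing the Visit 1 item is not needed. Protocol version 3.0 is dated 23 September 2019 and last patient in is planned for Q4 2019 (protocol section 6), so a change would reach few patients and make recording vary with calendar time.
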